^e Contact 7 is the last Follow-up contact; it should occur approximately 10 days after Contact 6.

CGM Initiation in People with T2D

4. Schedule of Activities

	Baseline (10 days)	Intervention (~50 days including the 10-day post-intervention period)			Post-Intervention Assessment & Study Completion (10 days)		Follow-Up Assessment (10 days)	
Study Phase	Phase 1					Phase 2		
Contact	1	2	3	4	5	6	7	
Visit Type	Clinic (Day -11)	Clinic	Remote	N/A	Clinic	Clinic	N/A	
Study Day(s)¹	-11 to -1	0	14 (+7)	40 (+7)	50 (+7)	170 (+14)	180 (+7)	
Consent	X							
HbA1c	X				X	X		
Demographics	X							
Up to 10-Day Blinded G7 CGM Assessment	X					X		
Blinded G7 CGM Data Downloaded and Saved		X					X ⁶	
ASA24 Diet Recall	X	X ⁴		X ⁵	X	X ⁵	X	
DietID Diet Recall	X				X			
PROs: Diabetes Distress, Diet Adherence, Efficacy Surveys, and Diabetes Self Care	X				X	X		
PROs: Intervention Fidelity and Post-Intervention Surveys					X			
Diabetes Medication Assessment	X	X	X		X	X		

CGM Initiation in People with T2D

BP, Weight, Height ²	X				X	X	
Randomization ³	X ³						
Participant Receives Randomization Assignment		X ³					
CGM Initiation / Education (based on randomization arm)		X	X				
Continuous Real-time G7 CGM Use							
Real-time G7 CGM Data Downloaded and Saved			X		X		
Up to 10-Day Real-time G7 CGM Assessment Begins				X			
Adverse Events						X	

¹ If indicated, up to seven or 14 days can be added to or subtracted from the specified contact date to allow for scheduling flexibility; ² Height at baseline only; ³ Randomization occurs for scheduling purposes only; the randomization assignment is not shared with the participant during Contact 1 and will not be shared at Contact 2 until a minimum of 7 days of blinded G7 CGM data are confirmed; ⁴ This ASA24 is considered part of the baseline assessment and should occur before any of the Contact 2 activities ⁵ Two ASA24 assessments on non-consecutive days should be completed during the post-intervention and follow-up periods, one should occur on approximately Day 40 and Day 170 and one on approximately Day 50 and Day 180 ⁶ Participants may have the option to return receivers via postal mail; if this occurs, data download will be delayed
							

5. Phase 1 Background

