1. Difference in total HEI score between groups during the post-intervention period	Automated Self-Administered 24-hour (ASA24 [®]) survey-derived total HEI-2015* score; score based on two diet recalls per assessment period, collected via web-based survey (ASA24 Version 2022 or later)

CGM Initiation in People with T2D

*Survey-derived HEI-2015 scores may be replaced with a newer scoring option if both scoring and analysis code become available

Exploratory Outcomes

Outcome	Assessment Method

1. Change in other CGM-derived core metrics from baseline to post-intervention; including as described by the 24-hour period, daytime period (6AM to 11:59PM), and nighttime period (12AM to 5:59PM):
 
 • number of days CGM device is worn • % time CGM sensor is active • mean sensor glucose mg/dL • % coefficient of variation • glucose management indicator (GMI) • % time above >250 mg/dL • % time above >180 mg/dL • % time below <70 mg/dL • % time below <54 mg/dL 	
See CGM-related outcome measures described above

2. Other CGM-derived metrics:
 
 • Change in % time in tight range (% time with glucose 70-140 mg/dL) from baseline to post-intervention • % of participants reaching CGM-derived consensus targets during post-intervention²⁶ 
 ○ % reaching >70% TIR (% time with glucose 70-180 mg/dL) ○ % reaching ≥5% improvement in TIR (% time with glucose 70-180 mg/dL) compared to baseline ○ % reaching >70% time TIR (% time with glucose 70-180 mg/dL) and reaching a ≥5% improvement in time in range compared to baseline 	
See CGM-related outcome measures described above

3. Describe HEI component scores by group during the post-intervention period
	
ASA24 survey-derived HEI-2015* component scores; scores based on two diet recalls per assessment period, collected via web-based survey (ASA24 Version 2022 or later)

4. Change in additional nutrition metrics from baseline to post-intervention
 
 • total energy intake • macronutrients and fiber 	
ASA24 survey-derived values based on two diet recalls per assessment period, collected via web-based survey (Version 2022 or later)

CGM Initiation in People with T2D

 select micronutrients 	

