
Baseline Assessment
	
 • PRO surveys (Diabetes distress, diet adherence, efficacy) • Participant wears G7 sensor paired with a physically blinded Dexcom receiver for up to 10 days and returns to clinic^b • Participant completes second ASA24 recall immediately before Contact 2 
^a As needed, participants will be contacted by study staff if their HbA1c does not meet inclusion criteria; instructions for sensor removal and options for returning the blinded receiver to the study team will be provided.
 
^b At least seven days of G7 sensor data must be obtained on the physically blinded Dexcom receiver. If a participant contacts the clinic to report the sensor has fallen off early/failed in fewer than seven days, the participant will be provided an option to return to clinic to pair another G7 sensor with the physically blinded Dexcom receiver, or the participant may choose to exit the study. Data from more than one G7 sensor may be an option to reach a total of seven days.

Contact 2: Participant receives randomization assignment and intervention begins
 
Day 0
 
Intervention
	
 • Eligible participants return to clinic with the physically blinded Dexcom receiver • Study team confirms at least seven days of CGM data were obtained* • Study team saves participant’s CGM data • Diabetes medication assessment • Participant receives randomization assignment • Participant applies G7 sensor and pairs it with apps on their personal cell phone • Participant receives CGM instruction based on study arm assignment, NFA or SDA • Participant wears the G7 sensor and uses the real-time glucose data from the associated apps until study completion • Study team documents measures of intervention fidelity 
*Confirmation of at least seven days of G7 sensor data is required before the participant can receive their randomization assignment. If seven days of G7 sensor data are not obtained, no Contact 2 assessments will be completed. The participant will be provided an option to pair another G7 sensor with the physically blinded Dexcom receiver and return for Contact 2 assessments in approximately 10 days, or the participant can choose to exit the study. Data from more than one G7 sensor may be an option to reach a total of seven days.

CGM Initiation in People with T2D

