	Mild (plasma glucose >250 mg/dl)	Moderate (plasma glucose >250 mg/dl)	Severe (plasma glucose >250 mg/dl)	Plasma glucose >600 mg/dl
Arterial pH	7.25–7.30	7.00 to <7.24	<7.00	>7.30
Serum bicarbonate (mEq/l)	15–18	10 to <15	<10	>18
Urine ketone*	Positive	Positive	Positive	Small
Serum ketone*	Positive	Positive	Positive	Small
Effective serum osmolality†	Variable	Variable	Variable	>320 mOsm/kg
Anion gap‡	>10	>12	>12	Variable
Mental status	Alert	Alert/drowsy	Stupor/coma	Stupor/coma

*Nitroprusside reaction method. †Effective serum osmolality: 2[measured Na⁺ (mEq/l)] + glucose (mg/dl)/18. ‡Anion gap: (Na⁺) – [(Cl⁻ + HCO₃⁻) (mEq/l)]. (Data adapted from ref. 13.)

Table taken from Kitabchi et al⁴³

Only reportable AEs and all SAEs will be recorded within an adverse event log with a description including the nature of the event, the date and time of onset and/or frequency, determination of non-serious versus serious, intensity (mild, moderate, severe), duration of the event, relationship to the intervention, the expectedness of the event, and outcome of the event. All reportable AEs and all SAEs will be reviewed and confirmed by a delegated medical doctor or equivalent. All AEs and SAEs must be resolved or deemed stable by a delegated medical doctor or equivalent before a participant completes or withdraws from the study.

Delegated study staff will report all reportable AEs, SAEs, and UPIRTSOs to the IRB in accordance with IRB policies.

22. Study Suspension or Discontinuation

This study will be suspended or stopped prior to completion if information becomes available during the study that indicates as such, this may include information related to adverse events or the potential for adverse events. The study may also be suspended or stopped prior to completion if recruitment

CGM Initiation in People with T2D

challenges or retention issues will impact the ability to properly analyze defined endpoints or for other reasons determined by the Investigator.

23. Statistical Considerations

Phase 1 Statistical Hypotheses

Primary Endpoint: Change in CGM-derived TIR (% time with glucose 70-180 mg/dL) from baseline to post-intervention.

Hypothesis (alternative): Participants randomized to a nutrition-focused approach (NFA) will show a larger increase in CGM-derived TIR from baseline to post-intervention than participants randomized to a self-directed approach (SDA).

Secondary Endpoint: Difference in total HEI score between groups during the post-intervention period.

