With an expected sample size of n=54 per arm for the intention to treat (ITT) sample in Phase 2, the primary analysis has 80% power ($\alpha=.05$, two-sided) to detect an absolute change for pooled study arms of 0.27 standard deviation units of change in TIR from the end of the intervention to follow-up. For within-arm tests of change in this sample the primary analysis has 80% power ($\alpha=.05$, two-sided) to detect an absolute change within a study arm of 0.39 standard deviation units of change in TIR from the end of the intervention to follow-up.

Populations for Analysis

The analysis for Phase 1 will follow a modified intention to treat perspective, with an analysis of CGM metrics that includes only participants with at least seven days of CGM data at both baseline (approximately day -11 to -1) and post-intervention (approximately day 40 to 50).

The analysis for Phase 2 will follow a modified intention to treat perspective, with an analysis of CGM metrics that includes only participants with at least seven days of CGM data at both post-intervention and follow-up. This sample is utilized to assess the effect of discontinuation of CGM utilized in phase 1. A per-protocol (PP) analytic sample will consist of participants with at least seven days of CGM data at both post-intervention and follow-up who did not use CGM, and who did not require changes to glucose-lowering medications during the follow-up period. This PP sample is utilized to assess the effect of discontinuation on patients not utilizing CGM and having no medication adjustments during the follow-up period.

General Approach for Statistical Analyses in Phase 1

Baseline characteristics of study participants will be summarized with mean and standard deviation for interval data and proportions for categorical data. For analyses that do not concern total HEI or HEI component scores, the analytic models will utilize general and generalized linear mixed model repeated measures analysis to estimate differential change by study arm from baseline to post-intervention period. The link function and error distribution selected for each model will be based on the distribution of the endpoint. Each model will include fixed effects for study arm, time, their interaction, variables used in stratification, and a random intercept for patient. Each model will report the model-derived estimate (and 95% confidence interval) for the endpoint by study arm and by time period (baseline, day 50).

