The key analytic test for the primary endpoint will be based on planned contrasts reflecting the interaction of study arm and time period and will report and test model-derived estimates of differential change by study arm along with 95% confidence intervals. For the primary outcome, statistical comparisons will be made between and within arms and for study arm by time interaction with significance assessed at $p < 0.05$. A final Statistical Analysis Plan will specify further analytic detail and inclusion of any additional covariates.

For analyses of total HEI score and HEI component scores, mean scores will be computed separately at

CGM Initiation in People with T2D

each time point (pre-intervention, post-intervention) and for each study group. Confidence intervals for means will be based on a Monte Carlo approach implemented with code developed for the HEI-2015 utilizing a population ratio method appropriate for ASA24 data (e.g. HEI2015_ASA24-2016_MC_PopulationScore.sas). Note: if additional versions of HEI scoring, coding, and analysis become available, these may be used (e.g. HEI-2022).

Analysis of Primary Endpoint

The analysis of the primary endpoint tests whether patients randomized to a nutrition-focused approach (NFA) will have a larger increase in CGM-derived TIR from baseline to post-intervention than patients randomized to a self-directed approach (SDA). A general linear mixed model repeated measures analysis will estimate differential change by study arm from baseline to post-intervention period in TIR. The analytic model will include fixed effects for study arm, time, their interaction, variables used in stratification, and a random intercept for patient. A final Statistical Analysis Plan will specify any additional covariates to be included in the model.

Analysis of Secondary Endpoint

The analysis of the secondary endpoint tests whether patients randomized to a nutrition-focused approach (NFA) will have higher total HEI score at post-intervention than patients randomized to a self-directed approach (SDA). Mean total HEI scores and 95% confidence intervals computed for each study group will be compared to understand study group differences.

Safety Analysis

The trial does not have formal safety endpoints or formal rules or statistical guidance on stopping due to safety concerns. The review and reporting of AEs and SAEs is detailed in the Assessment of Safety and Safety Reporting sections.

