Analysis of HEI component scores will include computing mean component scores and 95% confidence intervals for each study group; these will be compared to understand study group differences. Radar plots will be used to display differences. Summaries of intervention fidelity and potential behavioral mechanisms will utilize descriptive statistics computed within each study group.

Linear regression and Pearson or Spearman correlations will assess associations between TIR and HEI, HbA1c and HEI, participant perception of diet quality and calculated total HEI score. Additional analysis specifications involving study arm comparisons for exploratory endpoints and detailed specifications of other exploratory analyses will be described in a final Statistical Analysis Plan.

Analysis of Exploratory Endpoints in Phase 2

Exploratory endpoints are listed in the section Phase 2 Study Outcome Measures: Exploratory Outcomes.

Analysis of exploratory endpoints will follow the analytic framework for Phase 2 used for the primary endpoint and will report model-derived estimates and statistical testing of the change from the end of the intervention to follow-up period in the pooled study arms and within each study arm via pre-specified contrasts. Some exploratory analyses will be post-only analyses using the same analytic framework but will include only fixed effects for study arm and stratification factors, but not an effect for time. There will be no control for multiple testing in exploratory analyses. In sensitivity analysis, models will adjust for key prognostic factors selected a-priori.

Analysis of HEI component scores will include computing mean component scores and 95% confidence intervals for each study group at follow-up. Summaries of potential behavioral mechanisms will utilize descriptive statistics computed within each study group.

24. Data Collection and Management

Source data for the study will be collected verbally, physically, or electronically direct from the participant, from the participant's EMR, from the participant's G7 CGM system and the Clarity website, from web-based platforms where data is entered directly by the participant or with assistance of study staff (e.g. ASA24, DietID, REDCap, etc).

Study staff will record data in accordance with the UNITE Study MOP (UNITE MOP). Study data will be stored as follows:

- on paper case report forms
- in the participant EMR

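### The only secondary endpoint is analysed through two separate group intervals: no between-arm HEI difference is estimated or tested, and the baseline recalls are not used

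*Combined protocol and SAP*

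**What the plan says.** Section 23 (Phase 1 Statistical Hypotheses) gives the secondary endpoint as "Difference in total HEI score between groups during the post-intervention period", with the alternative that NFA scores higher. Under Analysis of Secondary Endpoint the stated purpose is a test of that alternative, but the only method is: "Mean total HEI scores and 95% confidence intervals computed for each study group will be compared to understand study group differences".

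The General Approach for Phase 1 keeps HEI out of the arm-by-time model used for the other endpoints: "For analyses that do not concern total HEI or HEI component scores, the analytic models will utilize general and generalized linear mixed model". HEI means are instead computed separately by time point and group, using a population ratio method with Monte Carlo intervals.

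Baseline diet data exist. Section 11 has each "score based on two diet recalls per assessment period". The second baseline recall is placed before the intervention visit in the footnotes to section 4 ("This ASA24 is considered part of the baseline assessment and should occur before any of the Contact 2 activities") and in the detailed schedule in section 15 ("Participant completes second ASA24 recall immediately before Contact 2"). Both baseline recalls are therefore due before the participant learns the arm.

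The exploratory analyses in section 23 also pair HEI with participant-level variables: "Linear regression and Pearson or Spearman correlations will assess associations between TIR and HEI".

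**The concern.** A test of a difference needs an estimate of that difference, its standard error and a rule for the conclusion. The secondary analysis supplies none of the three. Two intervals side by side invite the reader to look for overlap, which is a much stricter criterion than a 5% test.

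The comparison also ignores where each arm started. Randomization is stratified on HbA1c only (section 15), so diet quality is balanced by chance alone, and some of any chance imbalance carries into the post-intervention difference in proportion to the baseline-to-post correlation.

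HEI is the only secondary endpoint, and section 13 names dietary improvement as the reason to expect a greater gain in time in range with NFA. An inconclusive HEI result caused by the method of comparison would weaken the explanation of the primary result.

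**Working it through.** **Inputs.** Section 23 gives no standard deviation, effect size, power or analysis population for HEI. The only size to borrow is that of the primary endpoint: 60 per arm, 80% power, two-sided 0.05, difference 12.9 points, SD 25. That figure reproduces: n = 2 × (1.960 + 0.842)² / (12.9/25)² = 15.70 / 0.266 = 59 per arm by the normal approximation, and the t distribution gives power 0.800 at 60. N = 120 is used below for illustration. The correlation r between baseline and post-intervention HEI is not in the documents and is assumed over a range.

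**1. Judging by overlap of two 95% intervals** (a possible reading, not a stated rule). Let each group mean have standard error s, so that the difference has standard error s√2.
- Non-overlap requires a difference above 2 × 1.96 × s, which is 1.96 × √2 = 2.77 standard errors of the difference.
- Two-sided level: 2 × [1 − Φ(2.77)] = 0.0056, about 0.6%.
- A direct test has 80% power at a true difference of 1.960 + 0.842 = 2.80 standard errors. At that difference the chance of non-overlap in the right direction is Φ(2.80 − 2.77) = Φ(0.03), about 51%.

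**2. Using baseline HEI, participant-level scores.** Take the variance of a participant-level post-only difference as 1. A change score has variance 2(1 − r), and a baseline-adjusted difference has 1 − r². The detectable difference at 60 per arm is 2.802 × √(2V/60), which is 0.511 SD for post-only.

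| assumed r | change score | adjusted | variance saved by adjusting | detectable difference, adjusted |
|---|---|---|---|---|
| 0.2 | 1.60 | 0.96 | 4% | 0.501 SD |
| 0.3 | 1.40 | 0.91 | 9% | 0.488 SD |
| 0.4 | 1.20 | 0.84 | 16% | 0.469 SD |
| 0.5 | 1.00 | 0.75 | 25% | 0.443 SD |

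Estimating the slope multiplies the adjusted variance by about 1 + 1/(N − 4) = 1 + 1/116 = 1.009. Adjustment therefore costs under 1% even at r near zero, and breaks even at r = √(1 − 1/1.009), about 0.09. A change score, by contrast, is less precise than post-only whenever r is below 0.5.

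**3. Which r is plausible with two recalls.** Assume a single-day intraclass correlation of 0.2 to 0.4 and a true baseline-to-post correlation of 0.6 to 0.8. The reliability of a two-recall mean is 2 × ICC / (1 + ICC), or 0.333 to 0.571. Then r runs from 0.333 × 0.6 = 0.20 to 0.571 × 0.8 = 0.46, and adjustment saves about 4% to 21%.

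**4. Group ratio scores.** An illustrative simulation used 60 per arm, two recalls per period and a simplified four-component ratio score with made-up effects. Relative to post-only on the same scale, the adjusted variance was 0.990 for group ratio scores and 0.957 for participant-level scores; the change score gave 1.64 and 1.55. The two kinds of score also estimated different effects, about 6.0 and 3.5 points.

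**The case against.** The strongest reply is that the population ratio method yields one score per group and time point, so the planned analysis contains no participant-level HEI to put in a covariance model. This stands. A reader might infer that baseline adjustment is free precision; the documents do not support that. Moving to participant scores changes the quantity estimated, and the ratios in the table are relative to a participant-level post-only test that the plan does not propose.

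A second reply is that overlap is nowhere stated as the decision rule. That also stands: the 0.6% and 51% figures describe one way of reading the result. It does not remove the gap, because no other rule is given.

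A third is that the post-only comparison is unbiased under 1:1 randomization, its interval already allows for chance imbalance, and pre-intervention HEI by group would show an imbalance. This is correct, so inferring a biased result would go too far.

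A fourth is that section 23 defers further detail and covariates to a final statistical analysis plan. Those sentences sit with the general mixed-model text and the primary endpoint, and again with the exploratory endpoints. The secondary-endpoint text has none, and HEI is outside the mixed model.

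Finally, this is a pilot with no stated power for HEI. That limits how much the point matters, but a difference with its interval is what a later trial would take from it.

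**Conclusion.** The point holds as an efficiency and specification point about the secondary analysis. The firmer part is the missing between-arm difference with its interval and test. Its possible cost, power of about 51% instead of 80%, assumes roughly equal standard errors and a reader who requires non-overlapping intervals.

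The unused baseline is the lesser part. The saving is about 4% to 25% of variance for participant-level scores at an assumed r of 0.2 to 0.5, with the lower part of that range more plausible for two recalls, and it may be close to nil for group ratio scores. Larger gains need a higher correlation than the documents can support. The risk of adjusting is under 1% of variance at N = 120. Nothing here shows bias or an invalid comparison.

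**What to change.** Keep the population ratio scoring. Define the secondary analysis as the NFA minus SDA difference in post-intervention total HEI, with its 95% confidence interval and a two-sided test. Obtain these from a bootstrap that resamples participants within arm and HbA1c stratum; the Monte Carlo draws could serve for the unadjusted difference. Keep the group means and their intervals as the descriptive display.

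Resample each participant's baseline and post-intervention recalls together. The same run then gives a baseline-adjusted difference: the post-intervention difference minus b times the baseline difference, where b is the bootstrap covariance of the two differences divided by the bootstrap variance of the baseline difference. Draws made separately for each time point would not carry that covariance.

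Alternatively, report as a supporting analysis a covariance model of per-participant HEI on arm, baseline HEI and HbA1c stratum, and say that it estimates a somewhat different quantity. The planned correlations of HEI with time in range appear to need per-participant scores anyway. A change score should not be used in its place.

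The cost is a little more programming, a statement of which difference is the main one, and a rule for participants without baseline recalls, whom the unadjusted difference would still include. No data collection changes.
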